NON-INTERVENTIONAL (NI) STUDY PROTOCOL

Title	Evaluation of Xeljanz Access Barriers via Patient OOP Costs and TNFi cycling
Protocol number	Pfizer protocol ID A3921346
Protocol version identifier	Version number 1.1
Date	October 7, 2019
Active substance	L04AA29 (tofacitinib)
Medicinal product	Xeljanz (tofacitinib)

To evaluate the impact of (1a) Xeljanz index prescription OOP costs and (1b) TNFi cycling with etanercept and adalimumab vs. switching to Xeljanz on treatment persistence. Secondary Objectives: 2) To compare (1) high vs. low Xeljanz index prescription OOP costs, and, (2) TNFi cycling (2 groups) with etanercent and	Research question and objectives	Primary Objectives:
2) To compare (1) high vs. low Xeljanz index prescription OOP costs, and, (2) TNFi cycling		index prescription OOP costs and (1b) TNFi cycling with etanercept and adalimumab vs. switching to Xeljanz on
Xeljanz index prescription OOP costs, and, (2) TNFi cycling		Secondary Objectives:
 (2 groups) will etainetepi and adalimumab vs. switching to Xeljanz (2 groups) on: Differences in demographic and clinical characteristics. Treatment patterns including dosing, concomitant medication use, adherence, switching and a 6- factor effectiveness proxy measure (Curtis algorithm) between comparator cohorts. Post-index and change (Post-Pre) in All-cause and RA-related health care utilization associated costs. 		 2) To compare (1) high vs. low Xeljanz index prescription OOP costs, and, (2) TNFi cycling (2 groups) with etanercept and adalimumab vs. switching to Xeljanz (2 groups) on: Differences in demographic and clinical characteristics. Treatment patterns including dosing, concomitant medication use, adherence, switching and a 6- factor effectiveness proxy measure (Curtis algorithm) between comparator cohorts. Post-index and change (Post-Pre) in All-cause and RA-related health care utilization associated costs.

Author	PPD	, PharmD,MS
	PPD	, PPD PHI, Pfizer Inc.

2. LIST OF ABBREVIATIONS

Abbreviation	Definition
ADA	Adalimumab
AE	Adverse Event
AHRQ	Agency for Healthcare Research and Quality
ARRA	American Recovery and Reinvestment Act
CIRAS	Claims-based index for RA severity
CMS	Centers for Medicare & Medicaid Services
СОВ	Coordination of benefits
COPD	Chronic obstructive pulmonary disease
СРІ	Consumer price index
СРТ	Current Procedural Terminology
ED	Emergency department
ETN	Etanercept
FDA	Food and Drug Administration
GLM	Generalized linear model
HCFA	Care Financing Administration
HCPCS	Healthcare Common Procedure Coding System
HIPAA	Health Insurance Portability and Accountability Act
ICD-9/10 CM	The International Classification of Diseases, 9th and 10th Revision, Clinical Modification
IEC	Independent Ethics Committee
IRB	Institutional review board
ISPOR	International society for pharmacoeconomics and outcomes research
IV	Intravenous
LIS	Low income subsidy
MOA	Mechanism of action

Abbreviation	Definition	
MTX	Methotrexate	
NB-DMARD	Non-biologic disease modifying antirheumatic drug	
NDC	National Drug Code	
NIS	Non-interventional study	
NSAID	Non-steroidal anti-inflammatory drug	
OOP	Out-of-pocket	
PDC	Proportion of Days Covered	
RA	Rheumatoid Arthritis	
RAPID3	Routine assessment of patient index data	
RX	Outpatient pharmacy	
TNFi	Tumor-Necrosis Factor-alpha inhibitor	
TOFA	Tofacitinib	
UB	Uniform Bill	
US	United States	

4. AMENDMENTS AND UPDATES

5. MILESTONES

Milestone	Planned date
Start of data collection	21 December 2018
End of data collection	30 June 2019
Final study report	30 September 2019

6. RATIONALE AND BACKGROUND

Tofacitinib (Xeljanz) was approved by the US Food and Drug Administration (FDA) in November 2012 as the first oral JAK inhibit or for the treatment of adult patients with moderately to severely active rheumatoid arthritis (RA) who have had an inadequate response or intolerance to methotrexate. This advanced therapy may be used as monotherapy or in combination with methotrexate (MTX) or other nonbiologic disease-modifying antirheumatic drugs (NB-DMARDs). In February 2016, a once-daily Xeljanz XR formulation was approved, offering an option to the already approved twice daily immediate release formulation.

The most commonly used advanced therapies for RA are the Tumor-Necrosis Factor-alpha inhibitors (TNFi), in particular, adalimumab (Humira) and etanercept (Enbrel). Use of consecutive TNFis has been further reinforced by payer restrictions that often require failure of two or more TNFi's for receiving alternative MOA products like tofacitinib (TOFA).

However, there has been a growing body of largely observational evidence on the detriments of such TNFi cycling vs. switching to alternative MOA in patients with RA including:

- Shorter treatment persistence/duration;¹⁻⁴
- Higher likelihood of switching to third line advanced therapy;^{2,3,5}
- Higher costs;^{1,2}
- Lower effectiveness using 6-factor algorithm;^{2,3}
- Potentially poorer disease activity scores;^{4,6,7} however, further information on the impact of joint erosion associated with TNFi cycling vs. switching is not currently available.

In addition to step edits and prior authorization, another barrier to receiving advanced therapy for RA is the increased out-of-pocket (OOP) cost sharing for patients. An analysis of claims data for over 40,000 RA patients starting bDMARDs between 01/2004 and 12/2013 found that the average cost per prescription remained relatively unchanged, at approximately \$2300 per prescription, while OOP expenditures increased from \$36 (2.5%) per prescription to \$128 (7%).⁸ An analysis of insurance claims data for Medicare Advantage Part D patients with RA found bDMARD prescription abandonment (claim reversal without subsequent fill) ranged from 1.3% for the lowest out-of-pocket (OOP) cost group (\$0-\$250) to 32.7% for the highest OOP cost group (> \$550). Further, the odds of refilling bDMARD therapy were significantly lower for each OOP cost range (\$250.01-\$400.00, \$400.01-\$550.00, and >\$550.00) relative to OOP cost range of \leq \$250.⁹ An analysis of insurance claims for self-insured health plan members with RA starting etanercept or adalimumab demonstrated about 1 week of therapy lost per \$5.50 increase in weekly OOP expenditures. Those with weekly cost >\$50 were 58% more likely to discontinue than patients with lower OOP costs (hazard ratio 1.58, P<0.001).¹⁰ Additionally, Doshi et al¹¹

found using the 5% sample Medicare data that patients with RA belonging to a non-low income subsidy (LIS) group had a higher average OOP cost for Part D bDMARDs of \$484 (29.9% cost sharing) versus \$5 (0.3% cost sharing) in an LIS group which was associated with a 42% lower odds of filling Part D biologic agents while being more than twice as likely to receive Part B biologic agents and having a 31% lower odds of using any biologic agent vs. patients in the LIS group.

The current study is intended to evaluate the impact of restrictions on TOFA including OOP cost sharing and TNFi cycling with adalimumab and etanercept vs. switching to Tofacitinib on treatment persistence, treatment patterns, healthcare resource use, and costs.

7. RESEARCH QUESTION AND OBJECTIVES

The primary and secondary objectives will be evaluated using insurance claims for patients with rheumatoid arthritis (RA) identified in the Truven Health MarketScan database (see Section 8.4).

7.1. Primary Objectives

To evaluate the impact of (1a) TOFA index prescription OOP costs and (1b) TNFi cycling with etanercept (ETN) and adalimumab (ADA) vs. switching to TOFA on treatment persistence duration (see Section 8.3).

7.2. Secondary Objectives

To compare patients with (1) high (>median) vs. low (≤median) TOFA index prescription OOP costs, and, (2) TNFi cycling with ETN and ADA vs. switching to TOFA on:

- Differences in demographic and clinical characteristics;
- Treatment patterns including dosing, concomitant medication use, adherence, and switching, and a 6-factor effectiveness proxy (ie, Curtis algorithm) between comparator cohorts;
- Post-index and change (Post-Pre) in All-cause and RA-related health care utilization associated costs.

C

8. RESEARCH METHODS

8.1. Study Design

Т

[figure not shown]
This is a retrospective cohort study to evaluate patient characteristics, treatment patterns including a 6-factor effectiveness proxy measure, health care resource use and associated costs among RA patients initiating treatment comparator groups of interest between January 2014 and September 2016 across three US insurance claims databases. This period was selected since we typically have 5-year data license and wanted at least 2 years potential pre-index history, 2 years to capture treatment initation and 1 year for follow-up.

Further, we wanted to minimize channeling bias for TOFA in the first year of introduction where ADA and ETN were well established for a decade and based on prior analyses using 2012-2014 data indicating majority of TOFA use for 3rd line plus vs. ADA/ETN were mostly used for 2nd line treatment of RA (Chastek et al.² Poster presented at the ACR/ARHP Annual Scientific Meeting, San Francisco, CA, USA, November 6–11, 2015).

Figure 1. Study Diagram

Figure 1. Study Diagram

8.2. Setting

This study will leverage the de-identified, insurance claims database Truven Health MarketScan, between January of 2012 and September 2017. The database is further described in Section 8.4.

8.2.1. Inclusion Criteria

Patients must meet all of the following inclusion criteria to be eligible for inclusion in the study:

- 1. The **first pharmacy claim for TOFA and then ETN or ADA** between Jan 2014 and Sep 2016 represents the index claim *(See Appendix 1 for codes)*. Selection of comparator groups will be hierchical per the following:
 - a. First, select patients receiving ≥1 tofacitinib (TOFA) pharmacy claim (Jan 2014–Sep 2016) who did not have a TOFA claim anytime prior to index.
 - b. Amongst remaining patients, select those receiving ≥1 ETN or ADA pharmacy claim, assign per whichever occurs first, over same time period (Jan 2014-Sep 2016) who did not have a respective pharmacy or administration claim for index medication anytime prior to index.
- 2. Patients do have >1 advanced therapy filled on index date.

- 3. Physician diagnosis of RA (in any position) during the 1-year pre-index period, or on the index date:
 - ICD-9 = 714.0x-714.4x, 714.81;
 - ICD-10 = M05.x, M06.0–M06.3, M06.8–M06.9.
- 4. Patients don't have claims for other conditions for which TOFA and/or advanced therapies are used, during the anytime pre-index period or on the index date.

Disease	ICD-9 diagnosis code	ICD-10 diagnosis code
Ankylosing Spondylitis	720.0x	M45.0 - M45.9
Crohn's Disease	555.xx	K50.*
Psoriasis	696.1x	L40.0*-L40.4*, L40.8*-L40.9*
Psoriatic Arthritis	696.0x	L40.5*
Ulcerative Colitis	556.xx	K51.*

Table 1. Exclusionary Diagnoses

- 5. Commercially insured or Medicare beneficiaries at index.
- 6. Continuous enrollment during 1 (360 days)-year pre- (pre-index period) and 1-year post- index.
- 7. Age 18+ years at index.
- 8. Study cohorts.
 - a. TOFA Advanced Therapy Naïve OOP Cost Cohort.
 - Identify those with no advanced therapy (bDMARDs/JAK inhibitors) anytime before index TOFA prescription.
 - b. ETN or ADA to TOFA OOP Cost and TNFi Cycling Cohort.
 - Identify those that had ADA or ETN, but not both, and no other advanced therapy anytime pre-index TOFA (*See Appendix 1*).
 - c. ADA to ETN TNFi Cycling Cohort.

- In those newly starting ETN, patient must have a claim for ADA and no other advanced therapy (*See Appendix 1*), including index ETN (pharmacy/admin claims), anytime pre- index ETN.
- d. ETN to ADA TNFi Cycling Cohort.
 - In those newly starting ADA, patient must have a claim for ETN and no other advanced therapy (*See Appendix 1*), including index ADA (pharmacy/admin claims), anytime pre- index ADA.

NOTE: Advanced therapy = TNFi and nonTNFi bDMARDs and JAK inhibitors; Alternative MOA medications= nonTNFi bDMARD and JAKi.

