8.3. Variables

There are two primary baseline periods of interest from which variables of interests will be evaluated: 1) 12-months fixed pre-index period and 2) a variable length baseline period is the maximal continuous enrollment window prior to index and at least 1-year pre-index. The primary post-index period is 12 months including the index date. Other observation periods are noted below.

Variable	Role	Data source(s)	Operational definition
Demographics (Table 1)		
Age	Baseline Characteristic	All	Age will be defined as of the index year.
Age groups	Baseline Characteristic	A11	Patients will be assigned to one of the following age groups based index age: 18–44, 45–64, and 65yo.
Gender	Baseline Characteristic	All	Gender will be captured from enrollment data.
Insurance type	Baseline Characteristic	All	Whether the patient was covered under a commercial or Medicare Supplemental (Truven DataType) insurance plan will be captured.
Plan type	Baseline Characteristic	All	HMO, EPO, GPO, etc via.
			PlanType.
Geographic region	Baseline Characteristic	All	The United States (U.S.) region in which the study patient is enrolled in a health plan will be determined and reported and states will be categorized into five geographic regions: Northeast, South, Midwest, West, Unknown (https://www2.census.gov/geo/pdfs/maps- data/maps/reference/us_regdiv.pdf).
Variable length baselin	eBaseline Characteristic	All	Identify the duration of variable length (ie, all available pre-index continuous enrollment) baseline period.

Variable	Role	Data source(s)	Operational definition
RA-Related Medication	Use in Pre-Index (Tabl	e 2)	
Pre-index biologic DMARD use	Baseline Characteristic	All	A count of unique (on different days) pharmacy/admin claims on different days for ADA/ETN will be created during the 12 month baseline period.
Time from last pre- index bDMARD to index	Baseline Characteristic	All	A variable for the interval between last ADA/ETN pharmacy/administration claim and index. Stratify by <3 mos, 3-<6 mos and 6-12 mos pre-index.
Time from first pre- index bDMARD to index	Baseline Characteristic		A variable for the interval between first ADA/ETN pharmacy/administration claim during the variable length baseline and index. Stratify by <6, 6-12, ≥12 mos.

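### Criterion 1b, as worded, indexes a cycler on the first TNFi started inside the window and so drops that patient, while a tofacitinib switcher with the same history is kept

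*Combined protocol and SAP*

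**What the plan says.** Section 8.2.1 requires patients to meet every listed criterion. Criterion 1 sets the index claim as the "first pharmacy claim for TOFA and then ETN or ADA" in January 2014 to September 2016, and selection is hierarchical.

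- **1a (TOFA):** "select patients receiving ≥1 tofacitinib (TOFA) pharmacy claim (Jan 2014–Sep 2016) who did not have a TOFA claim anytime prior to index"). ETN or ADA claims earlier in the window do not move this index.
- **1b (everyone else):** "select those receiving ≥1 ETN or ADA pharmacy claim, assign per whichever occurs first, over same time period (Jan 2014-Sep 2016"), limited to those "who did not have a respective pharmacy or administration claim for index medication anytime prior to index".
- **8b (switchers):** "Identify those that had ADA or ETN, but not both, and no other advanced therapy anytime pre-index TOFA". The prior TNFi may fall before or inside the window.
- **8c (ADA to ETN):** "In those newly starting ETN, patient must have a claim for ADA and no other advanced therapy" before the ETN index. 8d is the mirror image for ETN to ADA.

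Criterion 8 has no cohort for ETN or ADA starters without a prior TNFi, and no section lets a later start replace the index set at 1b. Section 8.3 plans strata of under 3, 3 to under 6, and 6 to 12 months since the last ADA/ETN claim. It also plans strata of under 6, 6 to 12, and 12 or more months for the interval between the "first ADA/ETN pharmacy/administration claim during the variable length baseline and index".

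**The concern.** A cycler by definition uses two TNFi drugs. If the first was started inside the window, the earliest ETN or ADA claim belongs to the wrong drug for this purpose: it is the drug the patient cycles from, not the one cycled to. Rule 1a does not do this to switchers, because it indexes on TOFA whatever came before.

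This affects the primary 1b contrasts in Section 8.7.1.1 (ADA to ETN vs ADA to TOFA, and ETN to ADA vs ETN to TOFA) on persistence days. Cyclers who left their first TNFi quickly would be removed over most of the window, while switchers who did the same would stay. Time on the first TNFi plausibly predicts time on the next drug, so the arms could differ in persistence because of selection alone. The limitations in Section 8.9 do not mention this.

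**Working it through.** The plan states no sample size, power or expected count for these cohorts (Section 8.5), so there is no figure to reproduce. The check follows the criteria patient by patient, then counts months.

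**1. Matched patients.** Each history ends once in ETN and once in TOFA. First new start means that 1b looks only at claims that begin a drug.

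| History | Second drug ETN, 1b as first new start | Second drug TOFA |
|---|---|---|
| ADA from Mar 2014, second drug Mar 2015 | Index is ADA, Mar 2014; no prior ETN, so 8d fails; index is not ETN, so 8c cannot apply. Dropped | Kept in 8b |
| ADA from Jun 2013, filled to early 2015, second drug Mar 2015 | ADA is not a new start, so index is ETN. Kept in 8c | Kept in 8b |
| ADA Jun-Nov 2013, second drug Feb 2014 | Kept in 8c | Kept in 8b |

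The first row is dropped on a strictly literal reading as well. The second row is dropped only on the literal reading, where any ADA fill in the window sets the index.

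**2. Month counts under first new start.** The window is 12 + 12 + 9 = 33 months. A cycler indexed t months after 1 January 2014, with a first-TNFi claim before that date, has an interval since first TNFi longer than t.

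- Under 6 months is possible only if t < 6, that is January to June 2014. The remaining 33 − 6 = 27 months (July 2014 to September 2016) have almost no cyclers in that stratum.
- For t ≥ 12 the interval is generally at least 12 months. This covers 33 − 12 = 21 months (January 2015 to September 2016).
- Switchers have no such bound.

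**3. Share lost (assumed inputs, not from the documents).** Let L be the time from first-TNFi start to second-drug start. If true switch dates are uniform over 33 months, a cycler at month t is kept when L > t, so

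share kept = E[min(33, L)] / 33.

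Take L = 1 month + an exponential with mean 12 (first-TNFi duration averaging 13 months) + a gap uniform on 0.5 to 3 months, set here at its mean of 1.75. Then

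E[min(33, L)] ≈ 2.75 + 12 × (1 − exp(−30.25/12)) = 2.75 + 12 × 0.920 = 13.8, and 13.8/33 = 0.42.

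Simulation of 40,000 cyclers per setting gave:

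| Mean first-TNFi duration (months) | Kept | Lost |
|---|---|---|
| 7 | 26% | 74% |
| 10 | 35% | 65% |
| 13 | 42% | 58% |
| 19 | 53% | 47% |
| 25 | 60% | 40% |

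A separate simulation used uniform first starts from 24, 60 or 120 months before January 2014 up to September 2016, and an exponential time to second drug with mean 9 to 36 months. It gave 35-75% lost. Matching TOFA switchers were kept at 100%.

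**4. Who remains.** In the 13-month setting, retained cyclers had a mean first-TNFi duration of 20.4 months against 12.9 for all cyclers. Across settings their mean index time was month 6 to 13, against 16.5 for all.

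**5. After the repair.** With the index placed on the second TNFi, all simulated cyclers are kept and mean index time returns to about month 16.5.

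**The case against.** The best defence is that all criteria must be met together and that 1b concerns selecting comparator groups, which for ETN and ADA are only the cycling cohorts. A programmer could then apply 8c and 8d first and take the earliest qualifying claim, losing nobody. That reading is possible, and loose drafting elsewhere (criterion 2 appears to lack a negation) makes a redundant phrase believable. But the text does not state that order. Since no patient can satisfy both 8c and 8d, the first-claim clause would then do nothing.

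Three stronger readings are tempting and are not supported.

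- *Any in-window refill of the first TNFi removes the cycler, so almost none remain.* The wording permits this, but the time-since-last strata in Section 8.3 suggest it was not intended. No conclusion here rests on it.
- *Short-history strata are empty by construction.* There are exceptions. Rule 1b assigns on pharmacy claims, so a cycler whose first TNFi was given only by administration claim still indexes on the second drug. The time-since-first variable also starts at current continuous enrolment. For example: ADA in 2013, an enrolment gap, re-enrolment January 2015, ADA again August 2015 and ETN January 2016 give a measured interval of 5 months. Both are probably uncommon.
- *Adjustment cannot help.* Index month and year are recorded (Section 8.3) and are candidate covariates (Section 8.7.4), so index-date differences can be modelled. Short first-TNFi histories remain a problem because few or no cyclers have them. Restricting the TOFA arm to matching histories would restore overlap, at the price of a narrower question.

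The study diagram and the programming plan could not be seen, so whether any patient was actually dropped is unknown.

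**Conclusion.** The concern stands as a defect in the written rule. Followed in the order given, 1b with 8c/8d excludes cyclers whose first TNFi was newly started by pharmacy claim inside the window, while 1a with 8b keeps switchers with the same history. Under the first-new-start reading, the arms of the primary 1b contrasts would differ by design in first-TNFi duration and index date.

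The matched-patient result and the direction of the selection follow from the text. The 27-of-33-month count also needs the first-new-start reading and allows for the exceptions above. The 35-75% loss rests on assumed durations and switch dates and shows scale only. The size and direction of any resulting bias in persistence cannot be derived from the documents.

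**What to change.** In Section 8.2.1, delete the clause in 1b that assigns by earliest claim. State that, among patients not selected at 1a, the index is:

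- for 8c, the first in-window ETN pharmacy claim with no earlier ETN claim and at least one earlier ADA claim;
- for 8d, the first in-window ADA pharmacy claim with no earlier ADA claim and at least one earlier ETN claim.

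Add that the first TNFi may start before or inside the window, as 8b already allows. No tie-break is needed, because meeting one definition rules out the other.

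The cost is one sentence and a change to the cohort program, with no new data. Version 1.1 is dated 7 October 2019, after the planned final report of 30 September 2019 (Section 5), so the cohorts may already exist. The sponsor should check the cohort program against this rule and rerun it if it differs.

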8.5. Study Size

The sample size for this study is fixed by the duration of the observation window. No formal sample size computation was performed. All patients who meet inclusion/exclusion criteria will be included in the analyses.

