8.7. Data Analysis

8.7.1. Primary Objectives

8.7.1.1. To Compare 12-month Post-Index Medication Persistence Duration (days) by TOFA Index Prescription OOP Costs and TNFi Cycling with ETN and ADA vs. TOFA Switching

For this objective both descriptive and multivariable analysis will be conducted. For the descriptive analysis, treatment persistence duration (days) with index medication at 12-months will be compared for those with low (\leq median) vs. high (> median) OOP costs and for those who switch from ADA to ETN vs. ADA to TOFA and ETN to ADA vs. ETN to TOFA.

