8.8. Quality Control

This is a retrospective study, so issues of quality control at study sites, eg, data queries, do not apply. Analyses are programmed according the specifications in the protocol, and if applicable, the statistical analysis plan and documented in a programming plan. Final deliverables are reviewed and verified by a second, independent programmer who may also perform double programming. All quality checks are documented in the programming plan.

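### Inclusion criterion 2 in Section 8.2.1 is inverted as written: it admits only patients who fill more than one advanced therapy on the index date and shuts out single-drug starters

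*Combined protocol and SAP*

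**What the plan says.** Section 8.2.1 opens with "Patients must meet all of the following inclusion criteria to be eligible for inclusion in the study". Criterion 2 then reads "Patients do have >1 advanced therapy filled on index date". The section has no separate exclusion list under which that sentence could be read as a ground for exclusion.

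Other parts of the plan that bear on it:

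- Criterion 1b, for patients starting etanercept (ETN) or adalimumab (ADA): "assign per whichever occurs first".
- Criterion 4 is a true negative rule: "Patients don't have claims for other conditions for which TOFA and/or advanced therapies are used".
- Criteria 8a to 8d define the cohorts by which advanced therapies were used before the index drug. They do not address a second drug on the index date.
- Section 8.3 counts the index date as part of the 12-month post-index period. It defines an immediate switch as starting a non-index advanced therapy before a 60-day gap has run out, timed as switch date minus index date plus 1. Item 3 of the effectiveness proxy fails any patient who uses a different biologic or JAK inhibitor during follow-up.
- Section 8.7.1.1 sets the primary contrasts by index drug: "for those who switch from ADA to ETN vs. ADA to TOFA and ETN to ADA vs. ETN to TOFA".
- Section 8.5: "All patients who meet inclusion/exclusion criteria will be included in the analyses". No sample size is calculated.

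On enrolment, criterion 6 requires one year (given as 360 days) before index, and Section 8.3 also sets one year as the minimum. Section 8.9 says that two years of continuous pre-index enrolment will be used, in part to capture earlier advanced therapy.

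**The concern.** In a claims study with no sample size target, the eligibility list alone defines the analysis set. An operative criterion that states the opposite of what is meant is therefore more than a cosmetic slip. The programmer must set the text aside and guess the repair.

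The guess matters for one group. Criterion 2 is the only rule on same-day multiple fills: criterion 1b gives no tie-break when ETN and ADA are first filled on the same day, and criteria 8a to 8d look only backwards. At stake is whether the written protocol describes the population analysed, and whether patients with two advanced therapies on the index date were handled as intended.

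The enrolment mismatch is a smaller, separate matter. Naive status and the status of one prior TNF inhibitor both depend on how far back claims can be seen, and Section 8.9 offers two years as a safeguard that the eligibility rule does not require.

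**Working it through.** The plan states no sample size, power or event figure, so there is no number to reproduce. Two checks apply: the logic of criterion 2, and the day counts for enrolment.

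**1. Criterion 2, by number k of advanced therapies filled on the index date**

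| k | As written (k > 1) | With 'not' restored (k ≤ 1) |
|---|---|---|
| 1 | ineligible | eligible |
| 2 | eligible | ineligible |
| 3 | eligible | ineligible |

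Criterion 1 already guarantees k ≥ 1. Because all criteria must hold together, the literal set is exactly the patients with k ≥ 2, and every patient with k = 1 is lost.

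**2. The literal set against the plan's outcomes (Section 8.3)**

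- *Effectiveness proxy.* All six items must be met. With k ≥ 2, a different advanced therapy is used on the index date, which lies inside follow-up. Item 3 then fails for every admitted patient, so nobody in any cohort could be classed as effectively treated.
- *Primary persistence duration, naive tofacitinib cohort (8a).* These patients have no earlier advanced therapy, so a second one on the index date is necessarily an initiation. Days to immediate switch = (index date − index date) + 1 = 0 + 1 = 1. Persistence duration takes the earliest event, so it is 1 day for every patient in this cohort, and the high versus low out-of-pocket comparison there has nothing to compare.
- *Cohorts 8b to 8d.* The second drug could be a refill of the earlier TNF inhibitor rather than an initiation, so the day-1 switch does not follow automatically. The item 3 failure still does.

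A rule that fixes one outcome at failure for everyone, and the primary outcome at one day in a whole cohort, cannot be the intended rule.

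**3. Which repair**

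- Inserting 'not' excludes same-day multiple fills and matches the negative form of criterion 4.
- Reading the symbol as ≥ would admit same-day multiple fills, but would only repeat criterion 1. The symbol ≥ also prints correctly in criteria 1a and 1b.

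The first reading is the better one.

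**4. Enrolment (minor item)**

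- Two years by the protocol's own year: 2 × 360 = 720 days, so patients with 360 to 719 days meet criterion 6 but not Section 8.9.
- Two 365-day years: 2 × 365 = 730 days, so the range is 360 to 729 days.
- Data start in January 2012 (Section 8.2). Taking 1 January, the earliest index date of 1 January 2014 has 366 + 365 = 731 days of look-back. Either rule is feasible, so the data window does not settle which is meant.
- Section 8.1 also mentions two years, but only as potential history, so it does not contradict criterion 6.

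**The case against.** The strongest reply is that this is an evident slip with no shown effect. Section 8.8 says "Analyses are programmed according the specifications in the protocol, and if applicable, the statistical analysis plan and documented in a programming plan", and adds "Final deliverables are reviewed and verified by a second, independent programmer". A literal run would discard all single-drug starters and would almost certainly be noticed. The intended rule can also be inferred from the rest of the protocol. All of that stands. A reader might infer that the wrong patients were analysed, or that the cohorts cannot be rebuilt from the protocol; the documents support neither.

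A second reply is that two passages a reader might cite as flat contradictions are not. Criterion 1b names one index drug but does not forbid another fill that day, and Section 8.7.1.1 groups patients by index drug without mentioning same-day fills. That is fair. The firm conflict is with the outcome definitions in Section 8.3.

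A third reply is that the cause is uncertain: a word or symbol may be missing only from the public copy, and Figure 1, the table workbook and the programming plan are not available to check. This cannot be fully excluded. However, the sentence is complete, shows no gap or blacking-out, and is not corrected in any visible text. The uncertainty is a reason to confirm the rule before rewording, not to leave it.

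On enrolment, the two-year sentence sits in the limitations section, which does not set eligibility. Section 8.3 already uses all available enrolment and records its length. That keeps the item minor.

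**Conclusion.** Criterion 2 is wrong as written and must be corrected. It is an internal inconsistency, not a design choice. Read literally, it removes every patient with exactly one advanced therapy filled on the index date, who are the patients the cohorts describe, and it conflicts with the effectiveness and persistence definitions.

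The practical size depends on what was programmed. If same-day multiple fills were excluded, results do not change and only the written rule is at fault. If they were admitted, the effect depends on how many there are, which the documents do not give. The conclusion rests on the 'meet all' instruction, on the index date counting as follow-up, and on a dropped 'not' being the cause. The last is an inference, though a well-supported one.

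The mismatch between one and two years is real but minor. Section 8.9 is probably the outdated sentence, since both operative sections agree on one year. The number of patients affected and the direction of any bias cannot be derived.

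**What to change.** Check the programming plan to confirm that patients with more than one advanced therapy filled on the index date were excluded. Then insert 'not' after 'do' in criterion 2. If the check shows that another rule was programmed, text and program must be reconciled before results are reported. Cost: one word and one check of the program; no new analysis if the two agree.

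Separately, state a single pre-index enrolment requirement in Sections 8.2.1, 8.3 and 8.9. If one year is the rule, correct the sentence in Section 8.9 so that it does not overstate the look-back for earlier advanced therapy. That costs one sentence. If two years is meant, criterion 6 and Section 8.3 must change and the cohorts be selected again, which the data window allows.
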